- 2. Inability or unwillingness to comply with the requirements of the protocol as determined by the investigator
- 3. Pregnancy, breastfeeding or use of non-reliable method of contraception
- 4. Subjects with history of chronic liver disease, chronic renal failure, heart failure, diabetes mellitus
- 5. Previous history of hypersensitivity to cholestyramine
- 6. Subjects with complete biliary obstruction, intestinal obstruction
- 7. Previous history of hypersensitivity to prednisolone or other steroid compound
- 8. Subjects with underlying infection (systemic fungal, tuberculosis, bacterial, malaria, viral hepatitis, ocular herpes simplex, HIV)
- 9. Subjects with psychiatric disorder
- 10. Subjects with gastrointestinal diseases (diverticulitis, fresh intestinal anastomoses, active or latent peptic ulcer, ulcerative colitis, abscess or other pyogenic infection)
- 11. Subjects with ocular disease (cataract, glaucoma)
- 12. Subjects with osteoporosis or osteoporotic fracture
- 13.Participation in another clinical trial/ receipt of investigational drug within 4 weeks prior to screening visit
- 14. Current use of cholestyramine or other bile acid resins (colestipol, colesevelam)
- 15. Current use of prednisolone or other steroid compound (hydrocortisone, dexamethasone)
- 16.Subjects with history of bronchial asthma, bronchospasm, peripheral vascular disease or adverse reactions to propanolol
- 17.Subjects with adverse reactions to carbimazole such as agranulocytosis, severe skin rash
- 18. Hypokalemia (Serum K⁺< 3.5mmol/L)
- 19. Thyroid storm defined as Burch Wartofsky score of >45

Test treatment, dose and mode of administration:

There are 3 treatment groups:

Group 1: Cholestyramine plus standard treatment

Group 2: Prednisolone plus standard treatment

Group 3: Standard Treatment only

Standard treatment consists of Tablet Carbimazole 30 mg daily and Tablet Propanolol 40 mg twice daily. The duration of treatment for each group will be 4 weeks.

Group 1: Cholestyramine plus standard treatment

Cholestyramine powder 4g twice daily, Tablet Carbimazole 30 mg daily, Tablet Propanolol 40 mg twice daily.

Group 2: Prednisolone plus standard treatment

Tablet Prednisolone 30 mg daily for week 1, 20 mg daily for week 2, 10 mg daily for week 3 and 5 mg daily for week 4, Tablet Carbimazole 30 mg daily, Tablet Propanolol 40 mg twice daily

Group 3: Standard Treatment only

Tablet Carbimazole 30 mg daily, Tablet Propanolol 40 mg twice daily

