Thyroid hormone is metabolized in the liver where it is conjugated to glucuronides and sulfates and excreted in the bile. Usually only 20% of circulating T₄ is excreted in the bile and released into the intestine and reabsorbed completing the enterohepatic circulation. However in the thyrotoxic states there is an increased enterohepatic circulation of thyroid hormones with an increased urinary and fecal excretion of both conjugated and FT_4^{9} . Cholestyramine is an anion exchange resin that binds T₄ in the intestine resulting in fecal excretion of T₄ thus reducing the enterohepatic circulation and absorption in hyperthyroidism. Cholestyramine has been used in cases of thyroid storm¹⁰. Cholestyramine has been studied as an adjunctive therapy to thionamides and found to be effective in reducing thyroid hormones rapidly. Solomon et al first studied the effects of cholestyramine powder (4g QID) on 15 thyrotoxic patients and shown a more rapid decline in all thyroid hormone levels in the cholestyramine group in the first 2 weeks (P<0.01)¹¹. Mercado et al similarly reported rapid decline in total and free T_4 and T_3 when cholestyramine 4g tds was added to methimazole and propanolol¹². Kaykhaei et al. demonstrated a similar efficacy with a lower dose of cholestyramine (2g BD vs 1g BD) with all patients in the cholestyramine group achieving euthyroidism in 4 weeks⁹. The main adverse effects are flatulence and constipation in 10% of cases and vomiting, diarrhea, indigestion, abdominal pain, abnormal stools, bloating, headache, and raised triglyceride levels in 1-10%, whereas muscle pain, raised liver enzymes and difficulty in swallowing are rare¹³. Patients in the trials above tolerated the drug well with only 2 reported hyperdefecation and complained of bad taste¹¹.

Steroids have been shown to be effective in controlling hyperthyroidism. It demonstrates immediate effects by inhibiting the conversion of thyroxine to triiodothyronine peripherally and also blocks the release of thyroxine from the thyroid gland. It may also have the potential to suppress the immune response

20

Confidential Date: 5th June 2017

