6.1 Potential Risks

Cholestyramine is a bile acid sequestrant that works by increasing the removal of bile acids from the body. The most common adverse reaction is constipation but most instances are mild, transient and controlled with conventional therapy. Other less frequent adverse reactions are abdominal discomfort, flatulence, nausea, vomiting and bleeding tendencies due to hypoprothrombinemia if use long term. Detailed information can be found on the drug leaflet attached at the appendix. Solomon et al. reported all patients tolerated cholestyramine without inordinate difficulty with 2 patients experienced hyperdefecation for a couple of days and all patients complained of the taste of the powders¹¹.

Prednisolone is a corticosteroid and work by modifying the body's immune to various conditions and decreasing inflammation. response In hyperthyroidism it reduces the conversion of T_4 to T_3 . The common adverse reactions include fluid retention, alteration in glucose tolerance, elevation in blood pressure, behavioural and mood changes, increased appetite and weight gain. There is a risk of hypothalamic-pituitary-adrenal axis suppresion and Cushing's syndrome if given long term. It may increase the risks related to infection but rate of occurrence increases with the dose of steroids. There may be an increase risk of peptic ulcer disease. If used long term may decrease bone density. In a meta analysis, the use of prednisone 35 mg daily for a mean 64 days increased the risk for diabetes (OR 1.7 (1.1-2.6) P= 0.02), hypertension (OR 2.2 (1.4-3.8) P =0.01), dermatologic effects (OR 4.5 (3.5-5.7) P= 0.001) but was not statistically significant association for peptic ulcer, bacterial sepsis, osteoporosis, psychosis and tuberculosis¹⁹. Steroids may cause muscle weakness from renal potassium loss and myopathy if taken long term but there are case reports of thyrotoxic periodic paralysis soon after glucocorticoid administration²². The detailed information regarding risks and adverse reactions to prednisolone can be found in the drug leaflet attached in the appendix.

The immediate risks foreseeable in this study would be the risk of iatrogenic hypothyroidism. However this risk is closely monitored and the event of

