8.4.2 Exclusion criteria

- 1. Inability or unwillingness to provide written consent.
- 2. Inability or unwillingness to comply with the requirements of the protocol as determined by the investigator.
- 3. Pregnancy, breastfeeding or use of non-reliable method of contraception.
- 4. Subjects with history of chronic liver disease, chronic renal failure, heart failure, diabetes mellitus
- 5. Subjects with history of peptic ulcer disease, upper gastrointestinal bleeding, diverticulitis or ulcerative colitis.

- 6. Subjects who have recently had live or attenuated virus vaccines
- 7. Subjects with current infection (systemic fungal, active tuberculosis, cerebral malaria, viral hepatitis, HIV)
- 8. Subjects with cataracts and glaucoma
- 9. Subjects with osteoporosis
- 10. Subjects with psychiatric disorders
- 11. Subjects with complete biliary obstruction, bleeding disorders, hypertriglyceridemia (fasting triglyceride levels > 300mg/dL)
- 12. Previous history of adverse reactions to cholestyramine or other bile acid sequestrants
- 13. Previous history of adverse reactions to prednisolone or other steroid compound
- 14. Current use of cholestyramine or prednisolone or other steroid compound
- 15. Participation in another clinical trial and/or receipt of cholestyramine or prednisolone within 4 weeks prior to screening visit.
- 16. Subjects with history of bronchial asthma, bronchospasm, peripheral vascular disease or adverse reactions to propanolol
- 17. Subjects with adverse reactions to carbimazole
- 18. Hypokalemia (serum K^+ <3.5 mmol/L)
- 19. Thyroid storm defined as Burch Wartofsky Score >45

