9.9 Assessment of safety

Safety data will be analysed for the data collected throughout intervention period and up to follow up period. The following endpoints will be collected:

- Number of subjects with adverse effects during the intervention period and follow up period (total duration 6 weeks)
 - Subjects will be asked to report about adverse reactions (specified in the protocol) at 2 weeks, 4 weeks of intervention period and 2 weeks after end of study treatment period.
 - Number of subjects with serious adverse events during intervention period and follow up period (total duration 6 weeks)
 - Subjects will be asked to report about SAE immediately during the intervention period and follow up period

Safety and tolerability assessments will consist of:

- Regular performance of physical examinations
 - 1. BP, PR, Temperature, Weight (kg)
- Regular monitoring of laboratory tests
 - FPG/ RPG, Electrolytes (Na⁺, K⁺, Urea, Creatinine), FT₄, FT₃, TSH
- Monitoring and recording all adverse reactions and serious adverse events

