11.1.4 Study treatment and visits

Study treatment (Visit 3 Week 2)

The investigator will perform the following procedures:

- 1. Medical history taking
- 2. Record any concomitant medication
- 3. Record any change of dose administration of study treatment and assess compliance
- 4. Record any AE or SAE
- 5. Perform physical examination including vital signs (BP, HR, Temperature, Weight)
- Obtain blood sample (total of 6 mls of blood will be sampled). Thyroid function test will be sent to central lab (Gribbles laboratory) whereas the others will be sent to respective site's laboratory. (FT₄, FT₃, TSH, FBS/RBS, Blood urea and serum electrolytes)
- 7. UPT for women of childbearing age
- 8. Complete relevant section/page of CRF
- 9. Dispense study treatment
- 10. Refer to the study activities table below

Study treatment (Visit 4 week 4)

The investigator will perform the following procedures:

1. Medical history taking

- 2. Record any concomitant medication
- Record any change of dose administration of study treatment and assess compliance
- 4. Record any AE or SAE
- 5. Perform physical examination including vital signs (BP, HR, Temperature, Weight)
- 6. Obtain blood sample (total of 6mls of blood will be sampled). Thyroid function test will be sent to central lab (Gribbles laboratory) whereas the others will be sent to respective site's laboratory. (FT₄, FT₃, TSH, FBS/ RBS, Blood urea and serum electrolytes)
- 7. UPT for women of childbearing age
- 8. ECG
- 9. Complete relevant section/page of CRF
- 10. Dispense study treatment
- 11. Refer to the study activities table below

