11.1.5 Follow up visit (Visit 5, Week 6)

Safety assessment to monitor for adverse events, monitor for symptoms and signs of adrenal insufficiency and monitor for iatrogenic hypothyroidism.

- 1. Medical history taking
- 2. Perform physical examination including vital signs
- 3. Record any AE or SAE
- 4. Obtain blood sample (total of 6 ml of blood will be sampled). Thyroid function test will be sent to central lab (Gribbles laboratory) whereas the others will be sent to respective site's laboratory. (FT₄, FT₃, TSH, Blood urea and serum electrolytes/ FBS or RBS)

Study Activities Table

	Screening	Baseline Assessment and Randomisation	Treat	ment	Follow up
Visit	1	2	3	4	5
Timeline (wks)	-1	0	2	4	6
Procedures					
Informed consent	Х				
Check eligibility	х				
Blood sample for screening ^a	х				
Randomisation		X			
Patient demographics	Х				
Medical History	х				
Complete physical exam	х				
Height (cm), Weight (kg)	х	Х	х	Х	Х
Vital signs (BP, HR, Weight, Temp)	Х	X	Х	Х	Х
FT ₄ & FT ₃ & TSH	х	X (central lab)	X (central lab)	X (central lab)	X (central lab)
TRAb levels		X (central lab)			
FBS/ RBS	Х		Х	Х	Х
BUSE	Х		Х	Х	Х
UPT ^b	х	X	Х	Х	
U/S Thyroid		Х			
ECG		Х		Х	
ECHO ^c		X			
Efficacy assessment			Х	Х	
Concomitant medication			х	Х	
Report AE and SAE			Х	Х	Х
Dispense study treatment			х	Х	
Assess compliance			х	Х	
Complete relevant section of CRF			X	Х	Х

^a HepBsAg, Anti HCV ab, HIV1/2 ab, FBC, BUSE/Creatinine, LFT, FBS/RBS, FLP. Written consent will be taken for HIV test. All blood tests on screening visit including thyroid function test will be sent to the respective site's laboratory.

^b For women of childbearing age

^c Only if clinically suggestive of thyrotoxic cardiomyopathy or has atrial fibrillation

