11.2 Criteria for stopping subject treatment

The investigator will discontinue a subject's taking of study treatment at any time if the subject:

1. Who no longer wishes to participate in the trial and wishes to withdraw from the study at any time

2. Experiences intolerable adverse reactions

3. Is diagnosed with any of the exclusion criteria during the intervention period

4. Develops hypothyroid during the intervention period (Hypothyroid is defined as symptoms of hypothyroidism coupled with elevated TSH > 4.7 mU/L and normal or low levels of Free T4 <9 pmol/L

In all these cases, the investigator and/or the treating physicial will if possible encourage the subject to continue with the follow up assessment and to allow the use of collected data in the analyses.

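### After screening the schedule has no liver enzymes or lipids, so asymptomatic changes the plan itself names cannot be ascertained; potassium and glucose go unmeasured from screening to week 2

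*Combined protocol and SAP*

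**What the plan says.** Section 9.9 gives the regular laboratory monitoring as "FPG/ RPG, Electrolytes (Na⁺, K⁺, Urea, Creatinine), FT₄, FT₃, TSH". Section 11.1.4 lists the blood tests at weeks 2 and 4 as "FT₄, FT₃, TSH, FBS/RBS, Blood urea and serum electrolytes", and the week-6 follow-up visit repeats that set. Liver function, fasting lipids and full blood count appear only in the screening list of section 11.1.1, in section 11.3.1 under the screening visit, and in footnote a of the Study Activities Table: "HepBsAg, Anti HCV ab, HIV1/2 ab, FBC, BUSE/Creatinine, LFT, FBS/RBS, FLP".

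The baseline visit (11.1.2) takes blood for thyroid function and TRAb, with no potassium or glucose. It takes place no more than one week after screening.

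On risk, section 6 lists for cholestyramine "raised triglyceride levels in 1-10" per cent of cases, and calls raised liver enzymes rare. For prednisolone, section 6.1 names altered glucose tolerance and "case reports of thyrotoxic periodic paralysis soon after glucocorticoid administration". Section 8.4.2 item 11 excludes "hypertriglyceridemia (fasting triglyceride levels > 300mg/dL"), and section 11.2 item 3 stops study treatment in a subject who "Is diagnosed with any of the exclusion criteria during the intervention period". The events that section 10.1.1 requires to be collected include diabetes and hypokalemia, each with a laboratory threshold, but no liver or lipid event.

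**The concern.** A raised triglyceride or liver enzyme without symptoms is found only by a blood test. The plan names both as effects of a study drug and then schedules no test that could show them on treatment. The safety tables would contain whatever unscheduled testing happened to find. In an open-label trial, the decision to order such a test could also differ between arms.

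Safety is the sole secondary objective (7.2), and section 6.2 says the study will give definitive safety information on both adjuncts. A reader of the results could take few or no liver and lipid events as reassurance that the data do not give.

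A lesser version of the problem affects potassium and glucose. Both are pre-specified events, but the pre-dose value may be a week old and the first on-treatment value comes at week 2. A change that arises and resolves in between is not seen. A low potassium at week 2 also cannot be cleanly separated from one that was already present at randomisation.

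**Working it through.** The plan states no figure for detection of safety events, so there is none to reproduce. The check sets the schedule side by side and then sizes the one named risk for which the plan gives a rate.

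**Schedule** (sections 9.9, 11.1.1, 11.1.2, 11.1.4, 11.1.5, 11.3.1 and the activities table, which agree on this point):

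| Test | Screening | Baseline | Week 2 | Week 4 | Week 6 |
|---|---|---|---|---|---|
| Liver function | yes | no | no | no | no |
| Fasting lipids | yes | no | no | no | no |
| Full blood count | yes | no | no | no | no |
| Potassium (urea and electrolytes) | yes | no | yes | yes | yes |
| Glucose | yes | no | yes | yes | yes |

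**Raised triglycerides on cholestyramine.** Inputs: n = 45 per arm (13.1); p = 1% to 10% (section 6).

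- Expected number affected = n × p: 45 × 0.01 = 0.45; 45 × 0.10 = 4.5.
- Probability of at least one affected = 1 − (1 − p)^n: 1 − 0.99^45 = 36%; 1 − 0.90^45 = 99%.
- Scheduled lipid tests after screening: none. Number detected by the schedule: 0, whatever the true rate.

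**What one on-treatment test would add.** If all 45 were tested and none was raised, the one-sided 95% upper bound would be 1 − 0.05^(1/45) = 6.4%. With 41 tested, the number the plan needs per group before its dropout allowance, it would be 1 − 0.05^(1/41) = 7.0%. That is modest, but it would rule out the upper part of the 1-10% range. An untested zero rules out nothing.

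**Potassium and glucose.** Screening to baseline is up to 1 week and baseline to first recheck is 2 weeks, so up to 1 + 2 = 3 weeks separate the last pre-treatment value from the first on-treatment value. After that there are three measurements, at weeks 2, 4 and 6.

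**The case against.** The strongest reply is that safety capture does not rest on the scheduled panel alone. Section 10.2 records all adverse events found by questioning, examination, laboratory test or other means. Serious events are reported immediately, and unscheduled tests are not barred. Raised liver enzymes are rare by the plan's own account. The 1-10% rate carries no dose or duration, so it may not apply to 4 g twice daily for 4 weeks. Section 6.1 ties steroid-related muscle weakness to long-term use, and the early signal it mentions, periodic paralysis, is a symptomatic event that would reach adverse event reporting.

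Most of this stands and limits the point. It does not remove it, because none of these routes finds a raised triglyceride or liver enzyme in a subject who feels well.

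Several stronger readings are tempting, and the documents do not support them:

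- A reader might infer that these risks will be reported as absent because they were not measured. No section codes an unmeasured value as no event. For potassium and glucose the inference is wrong: both are mandatory reportable events and are measured three times after randomisation.
- A reader might see a flat contradiction between the triglyceride exclusion and section 11.2 item 3. That item is reactive: it acts if a diagnosis is made and promises no repeat test. It covers cataract and osteoporosis in the same way, and neither is rescheduled. A week-4 test would also come too late to make the criterion operate during treatment.
- A reader might treat the missing blood count as a gap of the same weight. Agranulocytosis appears only as an example in a synopsis exclusion, "Subjects with adverse reactions to carbimazole such as agranulocytosis, severe skin rash", and all three arms receive carbimazole. The omission limits absolute description more than the comparison between arms.
- A reader might use the share of the prednisolone course taken by week 2 as a measure of missed events. No passage links potassium or glucose risk to cumulative dose.

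**Conclusion.** The point holds as one of ascertainment. The schedule cannot detect asymptomatic liver-enzyme or lipid changes after screening, and it may miss early transient changes in potassium and glucose. A low or zero count of these must not be read as evidence of safety, and section 6.2 claims more than the schedule can deliver.

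For triglycerides the size is 0.45 to 4.5 expected cases among 45 cholestyramine subjects, with none detectable from scheduled tests. This assumes that the plan's 1-10% applies to this population, dose and 4-week exposure. The plan does not say which triglyceride level that rate refers to, so it should not be equated with the 300 mg/dL exclusion limit. No number of missed potassium or glucose events can be given from the documents.

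The primary efficacy comparison is not affected. The change is worthwhile because safety is the only secondary objective and the improvement is cheap.

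**What to change.** In section 9.9, section 11.1.4 and the activities table, for outcome ascertainment only:

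- Add liver function and a fasting lipid profile at week 4 in all three arms, with a full blood count optional, on the blood already drawn for the site laboratory. The screening results give the pre-treatment values, and Group 3 gives the reference.
- In section 11.1.2 and the activities table, add site-laboratory potassium and glucose at the baseline draw.

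The costs are the assays, a request to fast at a week-4 visit that now accepts random glucose, and a separate site tube at baseline, because the baseline blood tests now listed go to the central laboratory. There will also be more laboratory abnormalities to review, and section 5.1 requires ethics committee approval for a non-administrative amendment. Visits now take 6 mL and section 11.3.1 allows 5 to 10 mL, so there is some room for the extra volume.

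If the week-4 tests are not adopted, state in section 9.9 and in the report that asymptomatic liver, lipid and blood-count safety is not assessed, and limit the claim in section 6.2 accordingly.

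Separately, ask the sponsor to reconcile section 8.4.2 item 11 and section 11.2 item 3 with the laboratory schedule, so that it is clear how, if at all, the triglyceride criterion is meant to work after randomisation. Which clinical rule should apply is for the sponsor to decide.

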10 ADVERSE EVENTS

10.1 Definitions

10.1.1 Adverse event (AE)

Any untoward medical occurrence in a subject administered an investigational product and which does not necessarily have a causal relationship with treatment.

An AE includes:

- 1. A clinically significant worsening of a concomitant illness
- 2. A clinical laboratory adverse event: a clinical laboratory abnormality which is clinically significant, i.e an abnormality that suggests a disease and/or organ toxicity and is of a severity active management, Active that requires management includes active treatment or further investigations, for example change of medicine dose or more frequent follow-up due to the abnormality.

The following should be reported as AE:

Treatment of emergent symptoms which include:

- Medical conditions or signs or symptoms that was absent before starting study treatment.
- In this trial the following events must be collected and reported:
 - 1. SAEs
 - 2. AEs leading to discontinuation of study drug
 - 3. Gastrointestinal symptoms
 - a. Constipation
 - b. Bloating
 - c. Diarrhea
 - d. Abdominal pain
 - e. Vomiting
 - 4. Diabetes
 - 5. Hypokalemia
 - 6. Hypothyroid

- The following abnormal laboratory values particularly to this study will be observed
 - Fasting plasma glucose more ≥7 mmol/L or Random plasma glucose ≥ 11.1 mmol/L
 - Serum K+ <3.5mmol/L
 - TSH above upper limit of reference range and FT₄ normal or below lower limit of reference range
- Any doubtful event should be treated as an AE.

